#### Treatment-emergent Adverse Events

Treatment-emergent adverse events (TEAEs) are all AEs occurring during the treatment period or a pretreatment event that worsens in intensity during the treatment period.

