### **10.2.2.1 Onset Date**

The onset date is the date when the first sign(s) or symptom(s) were first noted. For example, if the AE is an abnormal laboratory test (such as “platelets low”), the onset date is the date when the sample was taken. If the subject was hospitalized for meningitis, and symptoms such as fever, headache, and nausea started the day before the hospitalization, the onset date is the day symptoms presented versus day of hospitalization.

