16. A single lead EEG will be bipolarly recorded for 5 days using a wearable EEG patch (Epitel device). The EEG recording will be centrally evaluated by a qualified rater. Subjects will be trained in the use of the device by site personnel and will replace the EEG patch every 7 days. Subjects will receive the device at screening. On Days 8 and 20, the nurse who conducts the home visit will check positioning of the device. The device will be returned on the Day 26 clinic visit. This assessment is based on device availability.
17. The "lifetime" version of the C-SSRS will be used at screening, and the "since last visit" version will be completed at all other visits.
18. The UM-PDHQ is a 20-item clinician-administered questionnaire that quantitatively and qualitatively assesses hallucinations. The UM-PDHQ will be completed for any subject who reports hallucinations.
19. All AEs, irrespective of the relatedness to the study drug, will be captured from the time the ICF is signed through the EOS visit. All AEs should be followed until resolution, for 30 days after onset, for 30 days after the last dose of study drug, until the subject is lost to follow-up, or the subject withdraws consent, whichever occurs first. Serious adverse events (SAEs) will be reported up to 30 days after the last dose of study drug. A follow-up phone call will be made 30 days after the last dose of study drug for evaluation of any SAEs.
20. Concomitant medications and adverse events will be recorded by the visiting nurse on Days 8 and 20.

21. Study drug will be administered in the clinic on the morning of Day 1 and Day 26. Study drug will be administered on an outpatient basis on the evening of Day 1 and Day 26 and on the morning of Day 27.
22. Drug compliance will be assessed by a remote mobile technology monitoring application (AiCure).
23. Evaluation of drug compliance and dosing accuracy will be assessed by the visiting nurse.
24. Subjects will return all remaining study drug (including empty bottles) to the site via a prepaid mailer.

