$$\text{total study drug received (capsules)}/\text{total study drug expected(capsules)} * 100$$

Adverse Event

An adverse event is any unfavorable or unintended sign (including an abnormal laboratory finding), symptom, or disease temporally associated with the use of a medical treatment or procedure that may or may not be considered related to the medical treatment or procedure.

Serious Adverse Event

A serious adverse event (SAE) is any adverse event that results in death, is life-threatening, requires in-patient hospitalization or prolongation of existing hospitalization, results in persistent or significant disability/incapacity, is a congenital anomaly/birth defect observed in any offspring of the subject conceived during treatment with the study drug or is an important medical event.

Treatment-emergent Adverse Event

Treatment-emergent adverse events (TEAEs) are all AEs occurring during the treatment period or a pretreatment event that worsens in intensity during the treatment period.

Laboratory Abnormality

Per protocol, a laboratory abnormality is any clinically significant laboratory abnormality suggesting a disease or organ toxicity and which is of a severity requiring active management (i.e., changes of dose, discontinuation of drug, more frequent follow-up, medical treatment or a diagnostic investigation). Laboratory abnormalities may also be recorded as adverse events. While laboratory values are available in the clinical database, assessment of clinical significance is not captured. As such, for analysis purposes, laboratory abnormalities are considered to be any values that are outside of the reported normal range for a given laboratory test.

Treatment-emergent Laboratory Abnormality

Treatment-emergent laboratory abnormalities are all analysis defined laboratory abnormalities occurring in the treatment period that were not within the normal range at baseline.

Concomitant Medications

Concomitant medications are those medications or non-drug therapies taken on or after the initiation of study drug. This definition includes medications started prior to the initiation of study drug that continue to be used concomitantly with study drug.

Orthostatic Blood Pressure

Orthostatic blood pressure is defined as the difference from recumbent to standing in the systolic and diastolic blood pressure measurements.

Seizure Duration

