5.3.2.3. Adverse Events

Adverse events will be mapped to a Medical Dictionary for Regulatory Activities (MedDRA) preferred term and system organ classification, version 21.0. If a subject experiences multiple events that map to a single preferred term, the greatest severity grade and strongest assessment of relationship to study medication, as determined by the investigator, will be assigned to the preferred term for the appropriate summaries. Adverse events that have a missing severity will be classified as having the greatest severity. Adverse events that have a missing relationship will be classified as having the strongest relationship to study medication.

A summary of TEAEs will be presented to show the number and percentage of subjects with at least one AE, SAE, AESI, related AE, or Grade 3 or higher AE.

The occurrence of TEAEs will be summarized by treatment group using system organ class, preferred term, and severity. Separate summaries of treatment-emergent SAEs, AESI, TEAEs related to study drug, and TEAEs leading to the discontinuation of study treatment, and TEAEs by CX-8998 dose administered will be generated. Adverse events will be assigned to a respective CX-8998 according to the start date of the adverse event.

All TEAEs will be listed for individual subjects. The listing will show both verbatim and preferred terms, along with the system organ class and other data gathered regarding the event. All AEs that have start dates prior to the initiation of study treatment will be excluded from the tables but will be included in the listings.

Determination of treatment emergence will be determined according to the rules outlined in Section 3.3.5.

The following are considered AEs of special interest: increase in seizure frequency, new seizure type, and status epilepticus. Otherwise; seizures are not reported as AEs or SAEs.

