7. CHANGES IN THE PLANNED ANALYSES FROM THE PROTOCOL

Changes to the planned analysis from protocol:

The following endpoints will not be summarized:

- The change in frequency (number of seizures per hour) of absence seizures as defined by a 3-Hz spike and wave lasting for ≥ 3 seconds as determined by hyperventilation (HV)
- The frequency (number of seizures per hour) of absence seizures (based on 6.5-hour video-EEG)
- The time to absence seizures during HV

- The percent of subjects with a shift in the occurrence of absence seizure (e.g., from HV period 1 to HV period 2)
- The percent of subjects with an absence of photic response.
- Change in seizure duration (determined by ambulatory EEG)
- Change in spike-wave run duration (determined by ambulatory EEG)
- Change in spike-wave density (spike-wave %) (determined by ambulatory EEG)
- Proportion of subjects with 30% and 50% reduction in seizure frequency (responder rate) and proportion of seizure-free subjects (determined by ambulatory EEG)
- Seizure-free intervals in minutes (maximum and average determined by ambulatory EEG)
- Change in the Seizure-related Disability Assessment Scale (SERDAS)
- Change in the average weekly seizure frequency for each type of seizure self-reported by subjects in the daily seizure diary
- Changes in the number of seizures recorded with the Epitel device (based on device availability)
- Relationship between the EEG parameters and the PK of CX-8998
- Exposure-response and exposure-safety relationships using plasma concentrations of CX-8998 and its 2 primary metabolites (M01 and M02) in population PK/PD analyses

Should any additional deviations from the analyses specified in the authorized statistical analysis plan arise, such deviations will be documented in the final clinical study report.

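### SAP 5.3.2.3 keeps every AE that starts before treatment out of the tables, although the SAP and protocol definitions count those that worsen on treatment as TEAEs

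*SAP*

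**What the plan says.** SAP 3.3.7 defines TEAEs as "all AEs occurring during the treatment period or a pretreatment event that worsens in intensity during the treatment period". Protocol 10.2.1 has the same definition, including "a pretreatment event that worsens in intensity during the treatment period".

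SAP 5.3.2.3, which governs the AE outputs, states: "All AEs that have start dates prior to the initiation of study treatment will be excluded from the tables". Such events stay in the listings. For the table by dose it states: "Adverse events will be assigned to a respective CX-8998 according to the start date of the adverse event" (the word dose appears to be missing). On treatment emergence it states: "Determination of treatment emergence will be determined according to the rules outlined in Section 3.3.5". Section 3.3.5 deals with incomplete dates.

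On collection, note 19 to the schedule in SAP 1.2 states: "All AEs, irrespective of the relatedness to the study drug, will be captured from the time the ICF is signed through the EOS visit". SAP Section 7, on departures from the protocol, opens its list with "The following endpoints will not be summarized". The list contains only efficacy, EEG, diary, disability-scale and exposure-related items. The TEAE definition is not among them.

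**The concern.** The second half of the TEAE definition describes events that began before treatment, and the table rule removes events that began before treatment. Both cannot be programmed as written. A programmer who works from 5.3.2.3 would drop a worsened pre-treatment event; one who works from 3.3.7 would keep it. Nothing in 5.3.2.3 sends the programmer back to 3.3.7, and none of the criteria in 3.3.5 covers worsening.

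TEAEs are the first-listed safety endpoint in a study whose primary objective is safety. The exclusion can lower the table counts relative to the definition but cannot raise them. All the planned AE tables are TEAE tables, so a reader of the tables alone would not see that an event had been left out.

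**Working it through.** The plan gives no figure to reproduce. The check is a comparison of the rules, followed by a statement of scale.

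**Step 1. Can such events be in the database?** Yes. AEs are captured from consent (SAP 1.2, note 19), and screening runs from Day -28 to Day -1, so the pre-dose collection window is up to 28 days.

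**Step 2. Follow one event through the rules.** Take an AE that begins as mild in screening and becomes severe on treatment.

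| Rule | Kept as one record with its pre-dose start date | Worsening entered as a new AE |
|---|---|---|
| TEAE under SAP 3.3.7 and Protocol 10.2.1 | Yes | Yes |
| Start date before treatment | Yes | No, for the new record |
| Enters the TEAE tables under SAP 5.3.2.3 | No | Yes |
| Dose in table 14.3.1.4, assigned by start date | None | Dose at the new start date |
| Appears in listing 16.2.7 | Yes | Yes |

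The rules disagree only in the first column.

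**Step 3. Which column applies?** The documents do not say. Protocol 10.2.2.1 states: "The onset date is the date when the first sign(s) or symptom(s) were first noted". That sentence and its examples concern dating an event from its first symptoms rather than from a later hospitalization. They do not address a change in severity, so they do not settle the matter.

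**Step 4. Outputs affected in the one-record case.** SAP Section 10 plans tables 14.3.1.1 to 14.3.1.4 (4) and 14.3.2.1 to 14.3.2.3 (3). 4 + 3 = 7 TEAE tables are subject to the exclusion. An event affects only the tables whose content it meets.

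**Step 5. Scale.** SAP 3.1 plans up to 15 subjects. One reclassified subject changes an incidence by 1/15 = 6.7 percentage points. As an assumption, if fewer are treated: 1/10 = 10.0 points and 1/5 = 20.0 points. A preferred-term row moves only if the subject has no other treatment-emergent record of that term. The any-TEAE row moves only if the dropped event is the subject's sole TEAE.

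**The case against.** The strongest reply is that the two rules may never diverge in practice. Protocol 10.2.2.2 grades each adverse event, and no field for a date of worsening is described. If each record carries one grade, worsening becomes visible only when a second AE is opened, and that AE has its own on-treatment start date. SAP 5.3.2.3 already provides for several events under one preferred term. SAP Section 1 refers data-collection details to the eCRF, which is not part of the documents. This stands: the effect on counts is conditional, and it may be nil.

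A reader might infer from Protocol 10.2.2.1 that a worsened event must keep its pre-treatment start date, so that the tables will undercount. The documents do not support that. The section says nothing on severity. Also, SAP 1.1 reports that no subject enrolled under amendments 4 and 5, and the supplied protocol (video-EEG, no Day 27 dose) matches the description of those amendments, so its onset rule may not have governed data collection. The contradiction itself does not depend on the protocol version, because both conflicting rules are in the SAP.

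A reader might also infer that 3.3.5 replaces 3.3.7 and, because its AE criteria speak of dates after first dose, loses events on Day 1. That does not hold either. Section 3.3.5 presents its criteria as additional ones for missing dates, and the treatment period in 3.3.7 begins with the first dose, so Day 1 events after dosing are already covered. Loosening that wording could admit Day 1 events that began or ended before dosing.

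Finally, worsening of the underlying seizures is reportable in its own right as an AE of special interest (Protocol 10.2.1, SAP 5.3.2.3). The gap therefore mainly concerns other AEs.

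**Conclusion.** Wrong as written; severity minor. That the exclusion contradicts the TEAE definition is certain from the text, and neither SAP 3.3.5 nor Section 7 resolves or declares it. That any table count will change is not established. It requires an AE that starts between consent and first dose, worsens on treatment, and is held as one record with its pre-dose start date. The number of such events cannot be derived from the documents and may be zero.

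Even where it occurs, the consequence is limited. The study is open-label and descriptive, and the AE listing would show the event to anyone who reads it. The reason to act is that a rule for a primary safety endpoint should not conflict with that endpoint's definition.

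**What to change.** Three changes to SAP 5.3.2.3:

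1. Limit the exclusion to AEs that start before treatment and do not worsen in intensity during the treatment period.
2. Cite 3.3.7 as the TEAE definition, with 3.3.5 only supplementing it where dates are missing or partial.
3. In table 14.3.1.4, assign worsened pre-treatment events by the date of worsening. If the eCRF does not capture that date, show them on a separate line.

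The cost is a few sentences and one programming flag; no new table is needed. Counts may become slightly less favourable. If the eCRF already opens a new AE for worsening, the results do not change and the edit only removes the contradiction.

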5.3.2.4. Physical and Neurological Examinations

Data from the physical and neurological examinations will be listed.

5.3.2.5. Columbia Suicide Severity Rating Scale

Data from the C-SSRS will be listed.

5.3.2.6. Epworth Sleepiness Scale

Results from ESS will be listed.

5.3.2.7. UM-PDHQ

Data from the UM-PDHQ will be listed.

5.4. PHARMACOKINETIC ANALYSES

Descriptive statistics of analyte concentrations will be prepared by analyte (CX-8998, including, but not limited to, M01 and M02), visit, time point, and dose. Plasma concentration values reported as below the limit of quantification (BLQ) will be presented as “BQL” in the concentration data listing. Values that are BLQ will be treated as 0 at predose time points, and set to one-half of the lower limit of quantification (LLOQ) at post-baseline time points for summary purposes.

The following conventions will be used for the presentation of summary statistics:

- If at least 1 subject has a concentration data value of BLQ for the time point, the minimum value will be displayed as “BLQ”.
- If more than 25% of the subjects have a concentration data value of BLQ for a given time point, the minimum and Q1 values will be displayed as “BLQ”.
- If more than 50% of the subjects have a concentration data value of BLQ for a given time point, the minimum, Q1 and median values will be displayed as “BLQ”.
- If more than 75% of the subjects have a concentration data value of BLQ for a given time point, the minimum, Q1, median and Q3 values will be displayed as “BLQ”.
- If all subjects have a concentration data values of BLQ for a given time point, all order statistics will be displayed as “BLQ” and SD will be suppressed.

Individual plasma concentrations of all measured analytes, visit, dose, nominal time point, date and time of actual collection, and actual time elapsed will be listed by subject for all subjects in PK population analysis set.

6. PROTOCOL DEVIATIONS

Protocol deviations will be documented by the investigator or assigned staff. All deviations and reasons for deviations will be reported to the Sponsor as soon as possible. Deviations will be presented in a data listing.

7. CHANGES IN THE PLANNED ANALYSES FROM THE PROTOCOL

Changes to the planned analysis from protocol:

The following endpoints will not be summarized:

- The change in frequency (number of seizures per hour) of absence seizures as defined by a 3-Hz spike and wave lasting for ≥ 3 seconds as determined by hyperventilation (HV)
- The frequency (number of seizures per hour) of absence seizures (based on 6.5-hour video-EEG)
- The time to absence seizures during HV

- The percent of subjects with a shift in the occurrence of absence seizure (e.g., from HV period 1 to HV period 2)
- The percent of subjects with an absence of photic response.
- Change in seizure duration (determined by ambulatory EEG)
- Change in spike-wave run duration (determined by ambulatory EEG)
- Change in spike-wave density (spike-wave %) (determined by ambulatory EEG)
- Proportion of subjects with 30% and 50% reduction in seizure frequency (responder rate) and proportion of seizure-free subjects (determined by ambulatory EEG)
- Seizure-free intervals in minutes (maximum and average determined by ambulatory EEG)
- Change in the Seizure-related Disability Assessment Scale (SERDAS)
- Change in the average weekly seizure frequency for each type of seizure self-reported by subjects in the daily seizure diary
- Changes in the number of seizures recorded with the Epitel device (based on device availability)
- Relationship between the EEG parameters and the PK of CX-8998
- Exposure-response and exposure-safety relationships using plasma concentrations of CX-8998 and its 2 primary metabolites (M01 and M02) in population PK/PD analyses

Should any additional deviations from the analyses specified in the authorized statistical analysis plan arise, such deviations will be documented in the final clinical study report.

9. PROGRAMMING CONVENTIONS

- Page orientation, margins, and fonts: Summary tables, listings, and figures will appear in landscape orientation. There should be a minimum of a 1.25" boundary on the upper (bound) edge, and a minimum of a 1.0" boundary on the remaining three edges. Output should be printed in Courier New with a point size of 8. Titles may be printed using a larger font (e.g., point size 10).
- Identification of analysis population: Every summary table and figure should clearly specify the analysis population being summarized. Listings will be prepared for the ITT Population.
- Group headers: In the summary tables, the group headers will identify the summary group and the sample size for the indicated analysis population. Of note, the header's sample size does not necessarily equal the number of subjects actually summarized within any given summary module; some subjects in the analysis population may have missing values and thus may not be summarized.
- Suppression of percentages corresponding to null categories: When count data are presented as category frequencies and corresponding percentages, the percent should be suppressed when the count is zero in order to draw attention to the non-zero counts.
- Presentation of sample sizes: Summary modules should indicate, in one way or another, the number of subjects actually contributing to the summary statistics presented in any given summary module. As mentioned above, this may be less than the number of subjects in the analysis population due to missing data.
 - In the quantitative modules describing continuous variables (and thus presenting sample size, means, and standard deviations), the sample size should be the number of non-missing observations. The number of missing observations, if any, will be noted.
 - For categorical variables that are presented in frequency tables, the module should present the total count in addition to the count in each category. Percentages should be calculated using this total as the denominator, and the percentage corresponding to the sum itself (that is, 100%) should be presented so as to indicate clearly to a reviewer the method of calculation. The number of missing observations, if any, will be noted.
- Sorting: Listings will be sorted by subject number, date, and parameter, if applicable. If a listing is sorted in a different manner, a footnote will indicate as such.
- General formatting rules: Rounding for all variables will occur only as the last step, immediately prior to presentation in listings, tables, and figures. No intermediate rounding will be performed on derived variables. The standard rounding practice of rounding numbers ending in 0-4 down and numbers ending in 5-9 up will be employed.
- The presentation of numerical values will adhere to the following guidelines:
 - Raw measurements will be reported to the number of decimal places as captured electronically or on the eCRFs, not to exceed 4 decimal places.
 - Standard deviations will be reported to one decimal place beyond the number of decimal places the original parameter is presented, not to exceed 5 decimal places.

- Means will be reported to the same number of decimal places as the parameter, not to exceed 4 decimal places.
- Calculated percentages will be reported with no decimals.
- Dates will be formatted as DDMONYYYY. Partial dates will be presented on data listings as recorded on CRFs.
 - Time will be presented according to the 24-hour clock (HH:MM).

10. PROPOSED TABLES, LISTINGS, AND FIGURES

Summary Tables

Accountability and Baseline Characteristics

All Subjects Screened

14.1.1.1 Subject Disposition and Termination from Study

ITT Population

14.1.1.2 Protocol Deviations

14.1.2.1 Demographics and Baseline Characteristics

Safety Population

